9.2.1 Treatment Assignment Procedures

A randomization schedule will be developed prior to enrollment by [name], Director of the Study Design and Biostatistics Center at the University of Utah. Blocked randomization with block sizes of 4 or 6 will be used. Randomization will be stratified based on site (Utah or Alberta) and responder status after 2 SMT sessions to balance these variables. Sequentially-numbered, sealed envelopes will be prepared containing treatment group assignments. The randomization envelope will be opened by the site Study Coordinator after completion of all baseline procedures and the 2 SMT sessions.

Subjects cannot be blinded to study treatments. Because our purpose is to optimize protocols, not to evaluate the SMT efficacy, we will not use placebos or attempt to balance clinician time. Randomization assignment will not be revealed until baseline examination, the first 2 SMT

sessions, and the OSW assessment are complete to reduce potential bias by either the subject or research assistant. Follow-up assessments will be performed by a Research Assistant who will be blind to subjects' treatment assignments. Clinicians providing treatment cannot be blinded. The use of standardized protocols for all treatments and clinician-compliance audits throughout the project will minimize potential bias related to differential treatment application. The PI at each site will be able to break the blinding if necessary for participant safety considerations.

9.3 Definition of Populations

Intention-to-treat principles will be used with all participants analyzed in their randomized group regardless of compliance. We will compare compliance between groups and "per-protocol" secondary analyses may be considered if non-compliance is high or disproportionate between groups. A compliant treatment episode will be defined as receiving at least 80% of study sessions based on randomized group.

9.4 Interim Analyses and Stopping Rules

Because of the minimal risk of the procedures in this study we have not proposed any stopping rules. We have not defined any procedures for interim analyses to avoid the risk of inflating Type I error. We will monitor the occurrence of adverse events throughout the study. If the number of serious adverse events warrants, we will suspend enrollment and review the safety of the study procedures under the direction of the DSM board and NCCIH representatives.

9.5 Outcomes

Outcome measure for the primary and secondary hypotheses of the study are outlined below. These outcomes will not require any adjudication.

9.5.1 Primary and Secondary Outcomes

The outcomes used to address the primary and secondary hypotheses of this project are each collected at baseline, 1-week, 4-week and 3-month assessments.

Oswestry Disability Questionnaire (OSW): The OSW is a LBP-specific measure of function for patients with LBP assessed on a 0-100 scale, with lower numbers indicating better function. Our past research has found the ODQ to have high test-retest reliability (ICC = 0.90), good construct validity, and responsiveness to change for patients with LBP, with a minimum clinically important difference (MCID) of 6 points.

Numeric Pain Rating Scale (NPRS): A 0-10 NPRS ('0' no pain, and '10' worst imaginable pain) will be used to assess LBP intensity. The NPRS has excellent test-retest reliability. Our previous research has found the NPRS to be responsive to change with an MCID of 2 points for acute LBP.

Spinal Stiffness: Spine stiffness will be assessed with a mechanically-assisted indentation device developed by [name] and used in our previous research. The device consists of a motorized indentation probe supported by an external frame. The probe contains a compressive-tension load cell (Entran, Fairfield, NJ) connected in-series with the probe. Displacement of the probe is measured by a linear variable differential transformer (Honeywell International Inc., Morristown, NJ) attached between the probe and its external housing. Signals from the load cell and transformer are collected by customized LABview software (National Instruments, Austin, TX) at a collection rate of 200 Hz.

Spinal stiffness is assessed with the subject prone on a table with arms at the side and a neutral neck position. The examiner manually identifies and marks the L₃ spinous process, and positions the indentation probe over it. The subject is instructed to inhale and exhale comfortably, and hold their breath at the end of exhalation during indentation, which lasts about 5 seconds. Indentation involves advancement of the probe from a 5 N pre-load to 60 N final load maintained for 1 second, then the probe raises automatically. Three indentation trials are performed with mean values used

for analysis. Indentation data (force and displacement) are used to calculate stiffness variables. Global stiffness (GS) (N) is calculated as the slope of the force displacement curve between 5-60 N, representing stiffness of underlying tissues during indentation. Terminal stiffness (TS) (N/mm) represents peak applied force and resultant displacement of underlying tissues. We have found excellent within- and between-day reliability of stiffness measures made with this device (ICC = 0.98-0.99). A safety switch is provided to the subject and assessor that raises the indentation probe immediately if pressed, providing additional safety features.

Lumbar Multifidus Muscle Activation: Multifidus activation will be measured with brightness-mode ultrasound images using a 60mm, 2-5 MHz curvilinear array. We have previously reported excellent intra- and inter-rater reliability for these measures. The subject is prone with neck in neutral and arms overhead at about 120° of shoulder abduction. The ultrasound transducer is placed just lateral to the spinal midline and angled medially until a parasagittal view of the multifidus at the L₄-L₅ and L₅-S₁ levels is obtained. Images are acquired at each level with the multifidus at rest and during submaximal contraction elicited by the subject lifting the contralateral arm about 2 inches while holding a weight proportional to body weight. Images are acquired at the end of exhalation to minimize effects of respiration. Three images in each state are acquired and averaged. Images are stored and measured offline by a blinded rater using NIH (Bethesda, MD) Image J software (V1.38t). Offline multifidus thickness measures are obtained from determining the distance between the posterior-most aspect of the facet joint inferiorly and the plane between the multifidus and thoracolumbar fascia superior. Activation is calculated as the change in thickness from rest to submaximal contraction ($\text{Thickness}_{\text{contract}} - \text{Thickness}_{\text{rest}}$) / $\text{Thickness}_{\text{rest}}$). Research has shown these measures of multifidus activation have good concurrent validity compared to EMG activity of the muscle.

9.6 Data Analyses

Primary Aim 1: Spine stiffness and multifidus activation will be co-primary outcomes for evaluating effects of SMT protocol components on SMT mechanisms. The effect of intervention components (A additional SMT; B multifidus activation; C mobilizing exercises) on each outcome will be evaluated using linear mixed models to relate mean levels of each outcome at 1-, 4-weeks and 3-months to indicator variables to represent the main effects of each interventions (A, B, C) as well as each pairwise interaction between the interventions (AxB, AxC, BxC) and the 3-way interaction (AxBxC). 1-week assessment, which occurs just before randomization, will serve as the baseline for these analyses and the model will be assumed equal between the randomized groups. This model, sometimes referred to as a constrained longitudinal model, leads to adjustment for baseline levels as in analysis of covariance (ANCOVA), which has been shown to remove conditional bias in treatment group comparisons due to chance imbalances and improve statistical power over unadjusted comparisons. An unstructured covariance matrix will be used to account for correlation of serially measured outcome scores in the same subject. By using an unstructured covariance matrix, the model will constitute a special case of a general linear mixed model which avoids imposing specific assumptions concerning distribution of random effects. This modelling approach is recommended in randomized trials when the number of follow-up outcome assessments is small. Restricted maximum likelihood estimation will be used for estimation of parameters and their associated standard errors.

Linear mixed effects analysis will provide estimates and CIs for the following quantities for each outcome at both 4-week and 3-month assessments: a) Main effects evaluating effects of each of the 3 interventions while averaging over the levels of the other 2 interventions. b) Three pairwise interactions evaluating if the effect of an intervention differs between levels of another interventions, while averaging over levels of the 3rd intervention. Pairwise interactions will inform whether the effects of each intervention pair are additive, synergistic or antagonistic. c) 3-way interaction evaluating if each pairwise interaction differs depending on the 3rd intervention.

Adjusted means with CIs will be provided for each treatment combination. Interaction plots will be used to depict significant interactions and linear contrasts constructed to evaluate the effect of each intervention conditional on the presence or absence of the other intervention. To account for 2 primary outcomes, each of the hypothesis tests noted above will be performed with 2-sided $\alpha=0.025$ and confidence intervals will be constructed using a confidence coefficient of 0.975. The indicated comparisons at 4-weeks will be given primary emphasis in evaluating the effects of each intervention. Comparisons at 3-months will evaluate persistence of effects following intervention.

Primary Aim #2: The OSW and NPRS will be co-primary outcomes for evaluating the effects of the 3 SMT protocol components on patient centered outcomes. The same analytic approach described above will be used. To account for 2 outcomes, we will again apply a 2-sided $\alpha=0.05$ and 97.5% CIs for statistical inference.

Secondary Aim #1: It is unknown how early SMT response may affect response to additional intervention. We will examine this question by evaluating responder status after 1 week as a possible effect moderator by adding a main effect for responder status and interaction terms between responder status and the indicator variables for treatments (and treatment combinations) which are retrained in the final simplified models for the different outcomes developed using the BIC criteria for each of the co-primary outcomes for the primary aims 1 and 2. Statistically significant interactions between responder status and main effect and/or interaction terms between treatment intervention components will be interpreted as suggesting effect moderation. Recognizing that tests for interactions have limited statistical power, we will also fit the simplified models developed in Aims 1 and 2 separately under the presence and absence of each factor (dichotomizing using a median split for continuous factors), and graphically display the estimated treatment effects at both levels of responder status. Recognizing the potential for lower statistical power, the results of Secondary Aim #1 will be interpreted as exploratory.

Secondary Aim #2: In order to assess which intervention component combinations provide optimal outcomes, we will first simplify the fully saturated factorial analysis of variance model by comparing the Bayes Information Criterion (BIC) among all possible models including different combinations of main effects, pairwise interactions and the 3-way interaction which satisfy the hierarchical consistency constraint that the main effects corresponding to each term in a pairwise interaction are retained in models with pairwise interactions, and all component main effects and pairwise interactions are retained when considering the 3-way interaction. This will result in a more parsimonious model to increase statistical power. Then, using the simplified model, for each outcome we will use a simulation approach to derive simultaneous 97.5% CIs for all comparisons of estimated mean outcome under each possible treatment combinations (No further treatment, A, B, C, AxB, AxC, BxC, AxBxC). After ordering the treatment combinations in accordance with the observed mean outcome, the simultaneous CIs will be used to identify which combinations are statistically indistinguishable from the optimum treatment, thus identifying a set of candidate options for the best combination of treatments. This process will be applied for both mechanistic and patient-centered outcomes. We anticipate that more than one combination will be considered optimal for different outcomes, and that the combinations that are optimal will differ for different outcome measures. Our interpretation of optimized protocols will give preference to longer term outcomes (ie, 3-month scores) and patient-centered outcomes. We will also consider an application of the robust modelling approach to derive a model for the optimum combination of components as a multivariate function which jointly incorporates each the potential effect modification of week 1 responder status in the same model. This approach will estimate the combination of components providing the optimum expected outcome for each participant based on their responder status after 1 week.

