6.2.2.2 Baseline Assessments

Assessments involve collection of both mechanistic and self-report outcomes. Self-report

measures will be collected via REDCap (Research Electronic Data Capture), an NIH-supported, browser-based, software solution that allows researchers to create secure online forms for data capture, management and analysis. At each assessment participants will input data directly into REDCap. If a participant is unable to directly input data using a computer paper forms will be available with data uploaded at a later time.

The following assessments are collected at baseline:

- Demographic data will include age, sex, race/ethnicity, employment status and general medical and LBP history. Current medication use for LBP will be recorded. This information will be used for descriptive purposes and possible covariates in analyses.
- Physical examination will include spinal and hip range of motion and segmental mobility assessed with manually-applied posterior-anterior force.
- Oswestry Disability Index (OSW): a self-reported LBP-specific measure of function assessed on a 0-100 scale, with lower numbers indicating better function.
- Numeric Pain Rating Scale: a self-reported 0-10 rating of pain intensity ranging from '0' no pain, and '10' worst imaginable pain.
- Psychosocial Covariate Measures: will include Fear Avoidance Beliefs Questionnaire will be used to measure patients' beliefs about how physical activity and work may affect their LBP and perceived risk for re-injury. The Pain Catastrophizing and Pain Self-Efficacy short forms will be used to measure the extent to which people catastrophize in response to pain and their degree of confidence in the ability to function with pain respectively. These variables may serve as covariates in the analyses to control for psychosocial risk factors.

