6.2.2.3 Randomization

Following baseline assessment all participants will receive 2 SMT treatment sessions in the next week. Randomization to additional treatment will be done at the 1-week assessment. A randomization schedule will be developed prior to enrollment by co-investigator [name], Director of the Study Design and Biostatistics Center (SDBC) in the CCTS at the University of Utah. Blocked randomization with block sizes of 4 or 6 will be used. Randomization will be stratified based on site (Utah or Alberta) and responder status after 2 SMT sessions (based on re-assessment of the OSW) to balance these variables. At the 1-week assessment the study coordinator or research assistant will look up the participant in the study database and open the Responder & Randomization Status

form in REDCap. This form will display the Oswestry score from the baseline assessment and the calculation of score change. The percent change between baseline and 1-week scores determines responder status (>50% improvement = “responder”; <50% improvement= “non-responder”). Once the responder status is entered the study staff will select the randomize button on the screen to trigger study assignment based on the allocation table provided by the biostatistician, provided all of eligibility criteria are met and the participant has been assigned to one of the two study sites. If any of these criteria are not valid a warning message will be displayed indicating the criteria issue(s) and the randomization will not be completed.

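### The primary models omit site and responder status, the two factors that stratify randomisation, which may cost a little precision

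*Combined protocol and SAP*

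**What the plan says.** Section 6.2.2.3 states: "Randomization will be stratified based on site (Utah or Alberta) and responder status after 2 SMT sessions". Section 9.2.1 repeats this and gives the purpose: "Randomization will be stratified based on site (Utah or Alberta) and responder status after 2 SMT sessions to balance these variables".

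For Primary Aim 1, section 9.6 uses linear mixed models that "relate mean levels of each outcome at 1-, 4-weeks and 3-months to indicator variables to represent the main effects of each interventions" (A, B and C), together with the three pairwise interactions and the three-way interaction. The 1-week value serves as a baseline constrained to be equal across the randomised groups. No term for site or responder status is listed. For Primary Aim 2 the plan says: "The same analytic approach described above will be used".

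Responder status first enters a model in Secondary Aim 1, "by adding a main effect for responder status and interaction terms between responder status and the indicator variables for treatments", and it appears again in the extension described under Secondary Aim 2. Site is not mentioned in section 9.6.

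Section 6.2.2.2 names possible covariates. Of demographics, history and medication it says "This information will be used for descriptive purposes and possible covariates in analyses", and of the psychosocial scores "These variables may serve as covariates in the analyses to control for psychosocial risk factors". Neither statement covers the stratification factors.

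**The concern.** A factor important enough to constrain the allocation would normally also be in the primary model. If it predicts outcome and is left out, the variance it explains stays in the residual. The model-based standard errors and confidence intervals are then wider than they need to be. Where blocking has balanced the factor, the tests can also be slightly conservative. Section 9.6 justifies baseline adjustment by its effect on chance imbalance and power, and the same reasoning applies to the strata.

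A site difference is plausible because recruitment sources (section 4.3) and treating clinicians (section 10.3.1) differ between Utah and Alberta. For stiffness, multifidus activation and pain, responder status is not derived from the outcome's own 1-week score, so it may carry additional information. Interval width also matters under Secondary Aim 2, where simultaneous intervals decide which combinations remain candidates for the optimum.

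**Working it through.** **Step 1: Does the stated power already assume the strata?** The inputs from section 9.2 are 280 enrolled and 92% retained, so N = 280 × 0.92 = 257.6; 80% power; and the tabulated SDs and pre-post correlations r. Section 9.6 gives two-sided alpha of 0.025 for Aim 1. The same value is used here for the Aim 2 outcomes, to match their 97.5% intervals. With adjustment for the earlier score only:

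Detectable main effect = (2.241 + 0.842) × SD × √(1 − r²) × 2/√N

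| Outcome | SD | r | Recomputed | Stated |
|---|---|---|---|---|
| Global stiffness | 1.60 | 0.80 | 0.369 | 0.37 |
| Multifidus | 0.124 | 0.70 | 0.034 | 0.034 |
| Oswestry | 14.9 | 0.70 | 4.09 | 4.12 |
| Pain (NPRS) | 2.12 | 0.45 | 0.73 | 0.76 |

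Three outcomes reproduce closely. Pain does not, but its stated figure is the larger. The table therefore takes no credit for the strata.

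**Step 2: Gain from including them.** Let p be the share of the 4-week variance remaining after the 1-week score that the strata explain. The documents give no value, so a range is assumed.

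- SE ratio = √(1 − p)
- Equivalent extra participants = N/(1 − p) − N
- Gap needed from one evenly split factor, in residual SDs = 2√(p/(1 − p))

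| p | SE ratio | SE reduction | Equivalent extra N | Gap needed | Oswestry detectable effect, from 4.12 |
|---|---|---|---|---|---|
| 0.01 | 0.995 | 0.5% | 3 | 0.20 | 4.10 |
| 0.02 | 0.990 | 1.0% | 5 | 0.29 | 4.08 |
| 0.05 | 0.975 | 2.5% | 14 | 0.46 | 4.02 |
| 0.10 | 0.949 | 5.1% | 29 | 0.67 | 3.91 |

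Global stiffness has the thinnest margin (0.37 detectable against a target of 0.40). Its power at 0.40 is 86.5% without the strata, 88.3% at p = 0.05 and 90.0% at p = 0.10.

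**Step 3: Responder status and the Oswestry.** Section 6.2.2.3 says: "The percent change between baseline and 1-week scores determines responder status". Much of its information is therefore already in the adjusted 1-week Oswestry. This was simulated with 1,000,000 draws. The assumptions were SD 14.9, 1-week and 4-week means of 24.3, day-0 score at least 20, day-0 mean 40 to 44, and correlations of 0.70 for day 0 with week 1 and for week 1 with week 4. Alone, responder status explained 12% to 23% of the 4-week variance. After the 1-week score it explained 0.0%, 1.0–1.2% and 3.6–4.3% when the correlation between day 0 and week 4 was 0.49, 0.60 and 0.70. A second set of assumptions, with a day-0 mean of 38 and SD of 12, gave 0% to 5%. At 4.3% the detectable effect is 4.12 × √0.957 = 4.03; at 5% it is 4.02.

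**Step 4: Type I error and the cost if the strata are uninformative.** The simulation used 30,000 replicates per setting, n = 258, eight combinations, an assumed 2:1 site split and 40% responders, and ANCOVA on the 1-week score. Nominal alpha was 0.025 and the Monte Carlo standard error was 0.0009.

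- Strata omitted, simple allocation: 0.023 to 0.025.
- Strata omitted, blocks of 4 or 6: 0.025 at p = 0.01 to 0.05, and 0.020 at p = 0.10. Each block was filled with distinct combinations drawn at random. That is an assumption, because the plan does not say how eight combinations fit such blocks.
- Strata included: 0.023 to 0.027.
- Strata with no effect: including them multiplies the model SE by 1.004 (simple allocation) or 1.002 (blocks).

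**The case against.** The planned analysis is valid as it stands, so this is an efficiency suggestion whose size rests on an assumed p. That is correct.

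The upper part of the range is hard to reach through site. A constant site gap at weeks 1 and 4 is partly absorbed by the 1-week score, leaving a fraction √((1 − r)/(1 + r)) of it in residual SDs. That fraction is 0.33 for stiffness, 0.42 for Oswestry and multifidus, and 0.62 for pain. Dividing the gaps in Step 2 by these, p = 0.01 needs a raw gap of about 0.6, 0.5 or 0.3 SD, and p = 0.05 needs at least 1.4, 1.1 or 0.7 SD. Only a site difference in change after week 1 escapes this, and the common training and standardised protocols work against one. This stands, and it is why the low end is more plausible.

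Stratification also delivers part of the benefit without any model term. In a simulation with blocks of 8 and stratum effects of 0.3 SD, including the strata cut the model SE from 0.0927 to 0.0893 (3.7%), but the actual spread of the estimates fell only from 0.0911 to 0.0905 (0.7%). Where blocking balances the strata, the gain is therefore mostly a reported SE closer to the true one, and the participant equivalents in Step 2 overstate the loss in the estimator itself. That simulation showed no conservatism (type I error 0.026 without the strata, from 3,000 replicates). The other showed it only at p = 0.10.

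None of this gives a reason to leave the strata out.

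**Conclusion.** The concern holds and is minor. Both stratification factors are missing from the primary models for both aims, and no covariate statement elsewhere in the plan supplies them. Responder status is explicitly something added later. The omission of site is inferred from its absence from section 9.6.

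Including the strata would probably reduce the reported standard errors by about 0% to 2.5%, or about 5% at the far end of the assumed range. There is no bias or type I error inflation, and no power conclusion in section 9.2 changes. The size depends entirely on how strongly the strata predict the 4-week outcome beyond the 1-week score, which the documents do not give. The possible gain exceeds the possible loss of at most 0.4%.

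**What to change.** In section 9.6, state that the primary models for both aims include site and responder status as fixed effects, each crossed with time. The 1-week mean may then differ by stratum while remaining common to the randomised groups within a stratum.

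Two wording changes follow. Secondary Aim 1 should say that only the interactions with responder status are added, since its main effect will already be present. Secondary Aim 2 should say whether the strata are kept in every model in the BIC comparison; keeping them in all would be consistent with the primary models.

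The cost is SAP wording only: 2 binary factors × 3 time points = 6 parameters with about 258 participants, and no new data. Stating it in advance also removes a later choice about adjustment.

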9.2 Sample Size and Randomization

Based on our past trials, we project 95% retention at 4-weeks. We estimated standard deviations of each outcome based on patients in a similar project with analogous eligibility criteria, and conservatively estimated pre-post correlations to be 4%-7% smaller than the values in this study. Assuming a sample size of 316, of which 280 meet all eligibility criteria and 92% of enrolled participants are retained to 4 weeks, the table below displays minimum detectable effect sizes for a) main effects of each protocol component, b) pairwise interactions between components, c) comparison of mean outcome between two levels of one component at a fixed level of another component, d) main effects of the 3 components in subgroup analyses involving half the participants, and e) pairwise interactions between 2 components in subgroup analyses with half the participants. This sample size provides at least 80% power to detect the MCID or hypothesized effect sizes for the main effects of each component for all outcomes, and for analyses of main effects in subgroups and conditional comparisons for each outcome except global stiffness. Power is more limited for secondary aims, such as pairwise interactions within subgroups.

	Assumptions for Outcome Measures in Project			
	Global Stiffness (N)	Multifidus Activation (mm)	Oswestry	Numeric Pain Rating
Assumption				
Mean (SD)	5.55 (1.60)	2.60 (0.124)	24.3 (14.9)	5.06 (2.12)
Pre-post score correlation	0.80	0.70	0.70	0.45
MCID or hypothesized effect size from past work	0.40	0.074	6.0	2.0
Type of effect	Detectable Effect Size			
Main effect	0.37	0.034	4.12	0.76
Pairwise interaction	0.74	0.064	8.24	1.53
Conditional comparison	0.53	0.045	5.83	1.08
Main effect in 50% of subjects	0.53	0.045	5.83	1.08
Interaction in 50% of subjects	1.05	0.091	11.65	2.16

Table. Assumptions and detectable effect sizes informing sample size for the project.

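### Aim 1 splits alpha equally between two co-primary outcomes where Holm's step-down gives the same error control with equal or greater power; Aim 2 prints an alpha of 0.05 that contradicts the split and must be corrected

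*Combined protocol and SAP*

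**What the plan says.** Section 9.6 names two outcomes for each primary aim. For Aim 1: "Spine stiffness and multifidus activation will be co-primary outcomes". For Aim 2: "The OSW and NPRS will be co-primary outcomes".

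For Aim 1, every factorial effect (three main effects, three pairwise interactions, one three-way interaction) is tested on each outcome under this rule: "To account for 2 primary outcomes, each of the hypothesis tests noted above will be performed with 2-sided" alpha of 0.025. To match, "confidence intervals will be constructed using a confidence coefficient of 0.975". The word Bonferroni does not appear, but 0.05/2 = 0.025 is that split. Section 9.6 describes no step-down procedure.

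For Aim 2, Section 9.6 says the analysis follows Aim 1 and then states: "we will again apply a 2-sided $\alpha=0.05$ and 97.5% CIs for statistical inference". The interval level is that of Aim 1; the alpha is not.

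Secondary Aim 2 chooses among treatment combinations by another route. After model simplification by BIC, it will "derive simultaneous 97.5% CIs for all comparisons of estimated mean outcome".

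The power table in Section 9.2 rests on this: "Assuming a sample size of 316, of which 280 meet all eligibility criteria and 92% of enrolled participants are retained to 4 weeks".

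**The concern.** Under a fixed split, each outcome is held to 0.025 whatever the other one shows. Holm orders the two p-values for a contrast. The smaller is tested at 0.025 and, if it is significant, the larger is tested at 0.05. Everything that Bonferroni rejects is still rejected, and the pair's error rate stays at or below 5% for any correlation. The fixed split therefore gives up some power.

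That could matter where the plan is tightest. Global stiffness has a detectable main effect of 0.37 against a target of 0.40, and Section 9.2 itself excludes it from the 80% power claim for conditional comparisons.

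Aim 2 raises a separate matter. If 0.05 is applied to both outcomes as printed, nothing is split, and a test can be significant while its 97.5% interval includes zero.

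**Working it through.** **Inputs (Section 9.2).** SD, pre-post correlation and target effect are:
- global stiffness: 1.60, 0.80, 0.40
- multifidus activation: 0.124, 0.70, 0.074
- Oswestry: 14.9, 0.70, 6.0
- pain rating: 2.12, 0.45, 2.0

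Analysed number: 280 × 0.92 = 257.6. I use 256, which is 32 in each of the 8 cells. The correlation between outcomes is not given; 0 to 0.5 is assumed.

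**Standard errors.** A main effect compares half with half, so SE = SD × √(1 − ρ²) × 2/√256.
- Global stiffness: 1.60 × 0.600 × 0.125 = 0.120
- Multifidus: 0.124 × 0.714 × 0.125 = 0.0111
- Oswestry: 14.9 × 0.714 × 0.125 = 1.330
- Pain: 2.12 × 0.893 × 0.125 = 0.237

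Multiply by √2 for a conditional comparison and by 2 for a pairwise interaction.

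**Reproducing the plan's detectable main effects.** Detectable effect = (z for alpha + 0.842) × SE, with z = 2.241 at 0.025 and 1.960 at 0.05.

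| Outcome | Plan | At 0.025 | At 0.05 |
|---|---|---|---|
| Global stiffness | 0.37 | 0.370 | 0.336 |
| Multifidus | 0.034 | 0.0341 | 0.0310 |
| Oswestry | 4.12 | 4.10 | 3.73 |
| Pain | 0.76 | 0.730 | 0.663 |

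Three of the four reproduce at 0.025. Pain is about 4% off, on the conservative side. None reproduces at 0.05. The table, which covers both Aim 2 outcomes, was therefore built on 0.025.

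**Power under Holm.** An outcome is rejected if its p ≤ 0.025, or if its p ≤ 0.05 and its partner's p ≤ 0.025. With independent outcomes,

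power(Holm) = P(0.025) + [P(0.05) − P(0.025)] × partner's power at 0.025.

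The bracket is the most that can be gained, and the partner decides how much of it is realised.

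*Global stiffness, main effect.* 0.40/0.120 = 3.333. P(0.025) = Φ(3.333 − 2.241) = 86.3%; P(0.05) = Φ(3.333 − 1.960) = 91.5%.
- Multifidus at its target (power near 100%): 91.5%.
- Multifidus null: 86.3 + 5.2 × 0.025 = 86.4%.

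With 257.6 in place of 256, the figures at target are 86.5% and 91.7%.

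*Global stiffness, conditional comparison.* 0.40/0.170 = 2.357. P(0.025) = 54.6%; P(0.05) = 65.4%.
- Multifidus at its target (power 99.4%): 65.4%.
- Multifidus null: 54.6 + 10.8 × 0.025 = 54.9%.

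*Oswestry, if 0.025 is the intended starting point.*
- Conditional comparison: 6.0/1.881 = 3.190, giving 82.9% to 89.1% with pain at its target, and 83.0% with pain null.
- Pairwise interaction of 6 points: 6.0/2.660 = 2.256, giving 50.6% to 61.4% with a 2-point pain interaction (partner power 97.6%), and about 50.8% with none.
- Main effect: about 99% either way.

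Simulation at correlation 0.5 agrees with these figures to within about 0.2 points.

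**Error rate of the pair, both nulls true.** Bonferroni and Holm reject at least one outcome in exactly the same cases. The rate is 1 − 0.975² = 0.049 if the outcomes are independent, and about 0.047 by simulation at correlation 0.5. For Aim 2 read literally it is 1 − 0.95² = 0.0975 if independent, with a bound of 2 × 0.05 = 0.10.

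**The case against.** The strongest objection is that nothing in Aim 1 is wrong. The split is valid, and at the target effects all four main effects already exceed 80% power under it. The plan reports estimates with intervals, and a 97.5% interval agrees one-to-one with a test at 0.025. Holm breaks that agreement at its second step. All of this stands, and it is why the change is optional.

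A reader might infer that Holm would add 5 to 11 points across the board. The documents do not support that. Those are upper ends, reached only when the partner outcome responds to the same contrast at its full target. Sections 5.1.2 and 5.1.3 direct one exercise programme at multifidus activation and the other at stiffness, so a component that moves one mechanism and not the other is plausible. The gain is then 0.1 to 0.3 points. The interaction example also goes beyond anything the plan promises, since Section 9.2 claims no power for a 6-point Oswestry interaction.

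A reader might also infer that alpha is split in both aims. As printed, Aim 2 is not split. If 0.05 were truly meant there, Holm would be stricter than the plan and would gain nothing. The 97.5% intervals, the statement that the Aim 1 approach carries over, and the table check all point to 0.025 as the intent, but the text has to say so.

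Two further limits stand. When stiffness truly responds and multifidus does not, Holm raises the false-positive rate for multifidus from 2.5% to about 0.025 + 0.025 × 0.863 = 4.7% with independent outcomes; the pair stays within 5%. And the choice of optimized protocols under Secondary Aim 2 rests on BIC and simultaneous intervals, which Holm leaves unchanged.

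**Conclusion.** There are two conclusions of different weight.

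1. **The Aim 2 alpha must be corrected.** The printed 0.05 contradicts the 97.5% intervals beside it, the Aim 1 approach it says it follows, and the Section 9.2 detectable effects. Taken literally, it allows a pair error of up to about 10%.

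2. **Holm is a cheap, optional efficiency gain.** For global stiffness it is worth about 0 to 5 points on a main effect and 0 to 11 points on a conditional comparison, which still stays below 80%. If 0.025 was intended for Aim 2, it is worth 0 to 6 points on an Oswestry conditional comparison and 0 to 11 points on a 6-point pairwise interaction.

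These ranges rest on the Section 9.2 SDs, correlations and target effects, about 256 analysed participants, and an assumed outcome correlation of 0 to 0.5. The lower end of each range is a partner outcome with no effect; the upper end is a partner at its full target.

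Neither the present split nor Holm across two outcomes controls error over the seven factorial effects. As an illustration, 14 independent tests at 0.025 give 1 − 0.975¹⁴ ≈ 0.30.

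**What to change.** In Section 9.6, for each contrast in both aims, state: *Holm's procedure across the two co-primary outcomes: the smaller p-value is tested at 0.025 and, if significant, the larger at 0.05.* In Aim 2 this replaces the alpha of 0.05, which then applies only at the second step. If the sponsor prefers to keep the fixed split, the minimum change is to print 0.025 for Aim 2.

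Keep the 97.5% intervals for reporting, with a footnote that an outcome significant only at the second step may have a 97.5% interval that includes zero.

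The cost is one sentence per aim and one footnote, written before any unblinded analysis. No participants, visits or data are added, and the Secondary Aim 2 intervals do not change.
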